## **XI. Assessment of Safety**

A DSMB will monitor the study for the occurrence of adverse events (both serious and otherwise). A significant increase in the rate of adverse events would be cause for concern for the safety of participants in the study. Information on adverse events will be presented in several ways: (1) listings of serious adverse events with accompanying narrative summary by the PI; (2) summaries of adverse events by body system and type of event. This information will be presented to the DSMB.

Interim monitoring reports for the DSMB will include, but will not be limited to, such tabulations as:

1. Frequency of BSI and hospitalization
2. coagulation studies
3. liver profiles
4. renal profiles
5. Frequency of adverse events

The DSMB will meet at the start of the study, then after 5 patients have received treatment. Subsequent meetings will be at the discretion of the chair given the expected speed of recruitment and study medication administration.

The DSMB chair (or designee) will be asked to review SAE reports within 48 hours after initial receipt of the information by the investigator(s), to review the PIs assignment of SAEs as related or unrelated to treatment, to confirm the grading of any toxicities. This will also be reported to the site IRB and the study sponsor.

A safety analysis will be performed after approximately 5 patients have received treatment or, if enrollment begins slowly, 12 months after the first patient is enrolled. Safety data will be shared with the Data and Safety Monitoring Board (DSMB). An investigator in this study will not be a member of the DSMB. Members of the DSMB will receive safety data approximately every 6 months for review or more frequently if requested by the chair. Safety assessments will consist of vital signs, AEs, and laboratory evaluations. A cumulative listing of patient withdrawals, dose adjustments, and serious adverse events (SAEs) will also be reviewed. DSMB members will be notified of all SAEs reported expeditiously to regulatory authorities.

[name], Division of Gastroenterology, will act as the chair of the DSMB. There will be 2 other members appointed to the DSMB: a statistician ([name]) and a neonatologist ([name]), who are not involved in the conduct of the study. [name] will serve as the safety officer for this study. The safety officer is not a member of the DSMB and he is an expert on glutamine metabolism and use in children with chronic and persistent diarrhea.

### Study Monitoring

An investigational new drug (IND) application was submitted by the PI for the use of L-GLN in the management of infants with SBS. An independent monitor from the CCHMC Clinical Trials Office will conduct routine independent monitoring visits that shall occur one or more times during the period after study initiation but before study closeout. Guidelines for scheduling monitoring visits shall be determined according to the stage of development, complexity of the study, the rate of subject accrual and other factors. Monitoring visits are conducted for routine monitoring only and are intended to ensure that the protocol and applicable regulatory requirements are being followed, that subjects' rights and safety are protected, and to confirm data integrity and quality.

### XII. Adverse Events

An adverse event (AE) is any untoward medical occurrence in a patient participating in this trial. An adverse event can be an unfavorable and/or unintended sign (including an abnormal laboratory finding), symptom, syndrome or disease associated with or occurring during the use of an investigational product whether or not considered related to the investigational product.

A serious adverse event (SAE) is one that:

1. results in death
2. is life threatening
3. requires an inpatient hospitalization or prolonged existing hospitalization
4. is a persistent or significant incapacity or substantial disruption of ability to conduct normal life functions
5. is a congenital anomaly/birth defect
6. is an event that does not meet the above criteria but may jeopardize the patient or may require medical or surgical intervention to prevent one of the outcomes listed above.

## **IRB Notification of SAEs**

Per Institutional Review Board (IRB) Requirements, the Investigator will report serious adverse events to the IRB Office within the time period required at each institution (at CCHMC this is outlined in research policy R-18). All other adverse events that are not serious will be reported to the IRB at the time of continuing review, per IRB requirements.

AE's require prompt (within 7 days after knowledge of the problem) reporting to the IRB when meeting the following criteria:

- Any unanticipated problem involving risk to subjects
- Deviations from or changes to, the protocol to eliminate immediate hazards to the trial participants
- Changes increasing the risk to subjects and/or significantly affecting the conduct of the trial.
- All adverse drug reactions that are both serious and unexpected
- New information that may adversely affect the safety of the subjects or conduct of the trial.

These events will be reviewed by the safety officer and are required to be reported to the FDA within 7 calendar days of the sponsor's initial receipt of the information if characterized as fatal or life-threatening. Non-fatal or non-life threatening events must be reported in 15 calendar days or at the time for annual review (reporting will be based on the FDA criteria for reporting AEs). In addition, these events are to be reported to the IRB based on IRB reporting guidelines. .

## **Recording of Adverse Events**

Adverse event recording will begin after administration of study medication.

Diagnostic and therapeutic non-invasive and invasive (i.e. surgical) procedures will not be reported as adverse events. However, the medical condition for which the procedure was performed must be reported if it meets the definition of an adverse event, unless it is pre-existing (prior to initiating GLN).

Medical conditions/diseases present before starting drug are only considered adverse events if they worsen after starting treatment.

Symptoms of the original or targeted disease are not to be considered adverse events in this treatment. The following symptoms are indicative of underlying disease and will not be reported as adverse events: Malabsorption, growth failure, liver disease and BSI.

Abnormal laboratory values or test results constitute adverse events if they induce clinical signs or symptoms or require therapy. They are to be recorded on the Adverse Events CRF under the signs, symptoms or diagnoses associated with them. CA-BSI will only be reported as an adverse effect if the rate is higher than 20% of what is standard for the center.

As far as possible, each adverse event will be assessed by the Investigator with respect to its duration (start and end dates), the severity grade (mild, moderate, severe, life-threatening, fatal), its relationship to the drug (unrelated, unlikely to be related, possibly, probably and definitely related), the action(s) taken, the outcome (i.e. resolved, resolved with sequelae, continuing), gravity (SERIOUS or NOT SERIOUS), and expected/unexpected on the basis of drug insert.

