An early stopping rule pending further investigation for this study will be invoked if any of the following adverse events occur:

- The rate of BSI in SBS patients in either the GLN supplementation or the placebo is an absolute 20% higher compared to the historical rate in SBS patients. The rate of catheter associated BSI is assessed monthly in all SBS patients at both CCHMC and the University of Michigan as part of the current clinical improvement process, If the rate of the BSI is higher in either group by 20% then study enrollment will be halted until further evaluation by the Data Safety Monitoring Board (DSMB).
- If two subjects develop the same grade-3 adverse event (including liver function tests, coagulation profile) related to the study medication that is irreversible upon de-escalation (does not reverse after 10 days) or upon discontinuation of the study drug
- Any subject develops a related grade-4 adverse event.

Since this is a double blind placebo control design, the data will only be unmasked by the research pharmacy at the request of the DSMB, if any of the above events occur. The statistician on the DSMB will evaluate the data. The unmasked data will not be revealed to the investigators unless the DSMB requests that the study be terminated.

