### Grading (Severity) of Adverse Events

Each adverse event will be graded to describe its intensity according to the Severity scale listed for each AE found on the NCI's Common Terminology Criteria for Adverse Events Version 4.0.

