#### Relationship to Drug

For all adverse events that occur while the patient is on drug, the relationship to the drug must be assessed by the Investigator using the following scale:

- 1 = not related
- 2 = unlikely
- 3 = possibly related
- 4 = probably related
- 5 = definitely related

For Grade > 3 adverse reactions which are possibly (3), probably (4) or definitely (5) related to the drug, study medication should be discontinued as described above.

Please note: For safety data analysis, not related and unlikely are considered "not attributable;" possible, probable and definite are considered "attributable." Assessment of relationship to drug must be carried out by the Investigator according to the 5-point scale above.

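### Malabsorption and growth failure are excluded from adverse-event reporting with no exception for worsening, seriousness or relatedness, and the plan does not say how this fits its rule on worsening

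*Combined protocol and SAP*

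**What the plan says.** Recording of Adverse Events (protocol section XII) contains four statements that bear on the point.

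- On pre-existing conditions: "Medical conditions/diseases present before starting drug are only considered adverse events if they worsen after starting treatment".
- In the next paragraph, on the disease under study: "Symptoms of the original or targeted disease are not to be considered adverse events in this treatment".
- Then the named list: "The following symptoms are indicative of underlying disease and will not be reported as adverse events: Malabsorption, growth failure, liver disease and BSI".
- A later exception for one listed term: "CA-BSI will only be reported as an adverse effect if the rate is higher than 20% of what is standard for the center".

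The rest of the safety system starts from a recorded adverse event. Under Grading, "Each adverse event will be graded to describe its intensity". Under Relationship to Drug, "For Grade > 3 adverse reactions which are possibly (3), probably (4) or definitely (5) related to the drug, study medication should be discontinued". One limb of the Stopping Rules (section IX.D) begins "If two subjects develop the same grade-3 adverse event", and requires the event to be related and irreversible. Another limb is a single related grade-4 adverse event. Among the criteria for a serious event in section XII is that it "requires an inpatient hospitalization or prolonged existing hospitalization".

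**The concern.** Every infant in the randomized groups depends on parenteral nutrition at entry, so impaired absorption and poor growth are to be expected. Keeping the baseline condition out of the adverse-event file is sensible. The difficulty is that the list goes further: it has no limit for a child who deteriorates on treatment, is admitted because of it, or is thought by the investigator to be harmed by the product.

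This matters because the study product is given into the gut. Section VI lists greater stool output, through the osmotic load of the feed, as a potential effect of both glutamine and the alanine placebo, while noting that previous trials did not report it. The dose is 0.6 g/kg/day; the enteral tolerability in infants that the Background cites is at 0.5 g/kg/day. A site could attribute a gut effect of the product to malabsorption, and the list would then tell it not to report the event. A second site, applying the worsening rule, could record the same event.

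**Working it through.** The plan gives no figure to reproduce on this point. The check is a comparison of texts.

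**Step 1. Do the two rules conflict?** The rule on pre-existing conditions is worded as only-if. Strictly, that makes worsening necessary for an adverse event, without saying that every worsening is one. There are two readings:

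- The list is a specific carve-out from the general rule. The text is then consistent, and the exclusion of the listed terms is unconditional apart from what is excepted elsewhere.
- The worsening rule also governs the listed terms. A deterioration on treatment is then recordable, and the list covers only the baseline state.

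Nothing in section XII says which applies. The definitions of adverse and serious events, and the sections on IRB notification, grading, relationship, follow-up and expedited reporting, set general rules without stating that they override the list.

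**Step 2. What else protects each listed term?**

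| Term | Named safeguard elsewhere |
|---|---|
| BSI | Exception in Recording of Adverse Events; rate-based stopping rule (IX.D); DSMB tabulation (XI) |
| Liver disease | Withdrawal limit on INR or direct bilirubin (IX.B); liver function tests named in the grade-3 stopping rule (IX.D); liver profiles to the DSMB (XI) |
| Malabsorption | None that names it |
| Growth failure | None that names it |

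Two of four terms are covered: 4 − 2 = 2 are not.

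**Step 3. What does an excluded event miss?** If it is never recorded, it receives no grade and no relationship rating. It is absent from the adverse-event summaries sent to the DSMB. It cannot count towards the grade-3 or grade-4 stopping triggers or the discontinuation rule. It cannot reach expedited reporting, which applies to serious, unexpected and at least possibly related events.

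**Step 4. What remains visible?**

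- Increased stool output is not on the excluded list. Abnormal laboratory results are adverse events if they cause symptoms or need treatment, and the toxicity panel is monthly (IX.E).
- Safety telephone calls are scheduled on days 15, 45, 75, 105, 135 and 165.
- Growth is measured at each 30-day visit and compared by arm; length velocity is the primary outcome of Aim 2. The share of nutrition given enterally, readmissions and length of stay are also compared by arm.
- Hospitalization frequency goes to the DSMB, in a list that section XI leaves open-ended.
- A child can be withdrawn for prolonged enteral intolerance that prevents dosing, or in the child's best interest.

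None of these gives a severity grade or causality rating to the malabsorption or growth failure itself.

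**Step 5. Size.** The rule applies to all 36 infants with short bowel syndrome. The adverse-event stopping triggers are one infant (1/36 = 2.8%) or two infants (2/36 = 5.6%). These percentages only restate how small the triggers are. They do not measure how many events would be lost, and the documents give no basis for estimating that.

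**The case against.** The strongest reply is that this is an ordinary design choice. A general rule followed by a specific exclusion is consistent drafting, and the listed features are inherent in the disease. The list also does not look absolute: liver disease is on it, yet liver function tests appear in a stopping rule. The harms most likely to come from the product would surface under other terms. The two excluded features are themselves measured, growth as an efficacy outcome.

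Much of this stands. A reader might infer that the plan contradicts itself outright; the only-if wording does not support that, because the carve-out reading is coherent. A reader might infer that worsening absorption or growth would go unseen; Step 4 shows that it would not. A reader might also infer that one or two omitted events would decide whether the trial stops. The documents do not show that either condition would reach grade 3 or 4 (the grading scales are cited but not reproduced), and the triggers also require relatedness and, at grade 3, irreversibility.

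Two things survive. The carve-out reading removes the conflict only by leaving these two terms with no exception at all, and the exceptions written for BSI and liver tests do not extend to them. In addition, comparison by arm cannot replace event-level assessment: section VI assigns the osmotic risk to both products, so a harm common to both arms could leave no difference between them.

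**Conclusion.** The point holds in a limited form. As written, malabsorption and growth failure are outside adverse-event reporting without exception for worsening, seriousness or relatedness, and the fit with the worsening rule is left unstated. These are two of the four listed terms, and the two with no named safeguard. The gap is confined to severity grading, causality rating, the adverse-event stopping and discontinuation triggers, and expedited reporting of the conditions themselves. Its frequency is unknown.

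This rests on two assumptions: that a site would follow the list literally, and that it would label the deterioration as malabsorption or growth failure and not under another recordable term. A careful site might do neither. This is a cheap improvement to a stated safety rule. It does not show that the trial's monitoring as a whole fails.

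**What to change.** Add one or two sentences to Recording of Adverse Events:

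- Malabsorption and growth failure are exempt only at baseline severity or in their expected course, as judged by the investigator.
- An event is recorded as an adverse event, graded and rated for relationship if it worsens beyond that expected course after the first dose, meets a criterion for a serious adverse event, or is judged at least possibly related to the study product.

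The threshold should be worsening beyond the expected course. The Background reports poor growth in these infants despite adequate calories, so any worsening from baseline would capture much of the natural history and collide with the exemption.

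The cost is a few more disease-related entries and some reliance on investigator judgement. The attributable/not-attributable split already defined under Relationship to Drug would separate those entries in the safety analysis.

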### Grading (Severity) of Adverse Events

Each adverse event will be graded to describe its intensity according to the Severity scale listed for each AE found on the NCI's Common Terminology Criteria for Adverse Events Version 4.0.

#### Relationship to Drug

For all adverse events that occur while the patient is on drug, the relationship to the drug must be assessed by the Investigator using the following scale:

- 1 = not related
- 2 = unlikely
- 3 = possibly related
- 4 = probably related
- 5 = definitely related

For Grade > 3 adverse reactions which are possibly (3), probably (4) or definitely (5) related to the drug, study medication should be discontinued as described above.

Please note: For safety data analysis, not related and unlikely are considered "not attributable;" possible, probable and definite are considered "attributable." Assessment of relationship to drug must be carried out by the Investigator according to the 5-point scale above.

#### Gravity (Seriousness) of Adverse Events

Each adverse event is to be classified by the Investigator as SERIOUS or NOT SERIOUS.

### Follow-Up after Adverse Events

All adverse events will be followed until they are resolved or the patient's participation in the treatment ends (i.e., until a final report is completed for that patient).

In addition, all SAEs and those non serious events assessed by the Investigator as attributable (i.e. possibly, probably, definitely related to the drug) will continue to be followed even after the patient's participation in the treatment is over. Such events will be followed for 30 days post treatment. Resolution of such events is to be documented in the CRF.

### **Expedited Reporting**

SAE's require expedited reporting when meeting the following criteria:

- Serious
- Unexpected
- At least possibly related to the study agent or other protocol specific activity

Serious Adverse Events meeting the above criteria are required to be reported to the FDA as follows:

- If characterized as fatal or life-threatening, within 7 calendar days of the sponsor's initial receipt of the information
- If non-fatal or non-life threatening, within 15 calendar days.

In addition, the sponsor is required to submit serious adverse events to the DSMB for review, and serious adverse events requiring expedited reporting will be reported to the IRB concurrently.

Significant unplanned deviations from the protocol will be reviewed and will be reported as stipulated above.

### **XIII. Statistical Analysis Plan**

To assess the comparability of the two treatment groups, demographic and baseline data will be summarized for each treatment group. For continuous data, mean, standard deviation, median, min, max, first quartile and third quartile will be presented. Comparisons will be made using the two-independent sample t-test or the Wilcoxon Rank sum test, depending on the distribution of the variable. For categorical data, frequencies and percentages in each group will be presented. Comparisons will be made using Fisher's exact test. These tests will be conducted at the two-sided, 5% level of significance. In addition, demographic and baseline data for the control group will be summarized and presented as described above. The statistical analysis plan for each aim is presented below.

**Aim 1 Hypothesis:** Enteral GLN supplementation in infants with SBS after massive bowel resection for NEC will decrease BSI, and thereby decrease systemic proinflammatory cytokine concentrations.

The primary outcome variable is the incidence of BSI during the 6 months on GLN supplementation. BSI is defined as laboratory-confirmed, culture-proven bloodstream infections that meet the Centers for Disease Control and Prevention (CDC) definition. To compare the incidence of BSI during the 6 month time period, the percent of patients with at least one BSI will be calculated in each group. Since this is a pilot study, the desire is to detect a trend in improvement of BSI with GLN supplementation. Therefore the 2 groups will be compared using the Fisher's Exact test at the one-sided 10% level of significance which will indicate a significant trend. As an additional analysis, time to first BSI will be displayed using Kaplan-Meier (K-M) curves. The log-rank test will be used to test for differences in curves between treatment groups. Patients will be censored if they exit the study prior to having their first BSI. As a further exploratory analysis, time to multiple-event analyses techniques will be used to compare groups where the multiple events represent multiple episodes of BSI within patients.

Secondary outcomes include the following and will be tested at the two-sided 5% level of significance:

- 1) Plasma proinflammatory cytokine levels: TNF- $\alpha$ , IL1- $\beta$ , IL-6, and IL-8. Change from baseline values at 180 days will be computed for cytokine levels. Change from baseline to 180 days values will also be calculated for the flagellin and LPS IgG levels. Appropriate transformations of the data (e.g. log) will be done prior to calculating change from baseline in order to meet the assumptions of the analyses (i.e. normality, equal variance). Analysis of covariance techniques will be used to compare the change from baseline scores of the treatment groups. Covariates included in the analysis will be baseline value, age, gender, ostomy status, feeding type (formula, breast milk).
- 2) Length of hospital stay and number of readmissions: For length of hospital stay, treatment groups will be compared using the Wilcoxon Rank Sum test. For number of readmissions, either a Wilcoxon Rank Sum test or a Chi-Square test for homogeneity will be used to compare groups, depending on the variability of the number of readmissions.
- 3) Stool sIgA levels: Treatment groups will be compared using the random effects repeated measures analysis of covariance. The response variables for each of the parameters will be change from baseline. The time points included in the analyses will be 30, 60, 90, 120, 150, 180 days post-baseline. If required to meet the assumptions of the analyses (normality, equal variances), appropriate transformations will be used. Treatment groups will be compared at each individual time point using appropriate contrasts and the error term from the repeated measures model. Covariates will include baseline value, age, gender, ostomy status, feeding type (formula, breast milk).
- 4) Proportion of nutrition delivered enterally versus parenterally: The statistically analysis approach for this endpoint will be the same as for the Stool sIgA levels discussed above. Transformations appropriate for proportions may be used, if necessary, to meet assumptions of the analyses.
- 5) Plasma glutamine: The statistical analysis approach for this endpoint will be the same as for the proinflammatory cytokine levels discussed above.
- 6) Impact of level of compliance on outcome will be evaluated for a dose effect analysis.

**Aim 2 Hypothesis:** Enteral GLN supplementation will improve somatic growth parameters in Aim 1 patients.

- 7) The two treatment groups will be compared using the random effects repeated measures analysis of covariance for the following parameters: length velocity, weight velocity, mid arm circumference and head circumference. Length velocity and weight velocity will be analyzed as the post baseline scores. Mid arm circumference and head circumference will be analyzed as change from baseline. The time points included in the analyses will be 30, 60, 90, 120, 150, 180 days post-baseline. If required to meet the assumptions of the analyses (normality, equal variances), appropriate transformations will be used (e.g. log). Treatment groups will be compared at each individual time point using appropriate contrasts and the error term from the repeated measures model. Covariates will include baseline value, age, gender, ostomy status, feeding type (formula, breast milk). For length velocity and weight velocity, the baseline value will be the baseline length and weight values.

To evaluate the impact of BSI on the growth parameters listed above, point biserial correlation coefficients will be constructed overall and within each treatment group and tested to determine significance.

**Aim 3 Hypothesis:** The gut luminal microbiome is altered in pediatric SBS versus non-SBS controls, correlates with BSI and is altered by *enteral* GLN supplementation.

- 8) Intestinal microbial groups (e.g., species, genera) will be correlated with the treatment or control arms of the GLN supplementation trial and with bacteria identified during any diagnosed BSI. The frequency of rRNA sequences will be interpreted as the relative abundances of organisms in samples of stool and standardized by gram of stool weight. Bacteria present in specimens will be preliminarily identified by use of the Naïve Bayesian Classifier Tool of the Ribosomal Database Project. The strength of association of individual microbial groups with treatment arms and/or main outcome measures will be measured by comparing the abundances of these groups using the non-parametric Kruskal-Wallis test. Experimental reproducibility and inter- and intra-individual similarities in microbial populations will be assessed by calculating and comparing the sequence-abundance-based Morisita-Horn index. In all statistical analyses 2-sided *p*-values less than 0.05 will be considered statistically significant. Results will be corroborated through the phylogeny-based UniFrac metric, which assesses population-wide differences in microbial lineages between different groups of subjects (SBS vs. control). Stool-associated bacteria collected at BSI incidence will be compared to the species identified on blood culture to determine whether intestinal bacteria are potential sources for BSI. Alternatively, absence of particular species from the stool at the time of BSI diagnosis will indicate that lack of specific bacterial species from the stool predisposes to BSI. Tissue samples collected during endoscopy or surgery and intestinal fluid aspirated during endoscopy will be analyzed in parallel with stool samples in order to assess the use of stool samples as proxies for intestinal samples. Patterns will also be reviewed to assess for relationships to enteral feeding rate.

These methods have been used and demonstrated in 2 published studies by one of the collaborators/co-investigators.

